### 5.2.4. Analysis of Primary Endpoint

The difference in Day 28 CR/PR rates between arms will be estimated along with a 90% confidence interval. Note that patients classified as high risk per biomarker results and patients with missing biomarker results will be excluded from the primary analysis. In addition to the difference in rates, within arm CR/PR rates will be estimated with accompanying confidence intervals.

### 5.2.5. Analysis of Secondary Endpoints

Given the large number of secondary endpoints, a significance level of 5% will be used for all comparisons (and 95% confidence intervals). This provides some control of multiplicity without overly restricting the study's ability to detect differences.

1. Proportion of Patients with CR/PR and Steroid Dose 0.25 mg/kg or less This is a key secondary endpoint of the trial. The rates will be estimated within each arm and comparison between arms will occur using the Z test for binomial proportions (or Barnard's Exact Unconditional as appropriate).

#### 2. Proportion of response

Proportions of complete, partial (PR), mixed response, no response and progression among surviving patients at Day 14, 28 and 56 will be compared between the treatment groups using the chi-square test (or Fisher's Exact as appropriate).

### 3. Treatment Failure

Proportion of primary treatment failures at Days 14, 28 and 56 will be compared using the Z test for comparing binomial proportions (or Barnard's Exact Unconditional test as appropriate).

4. Incidence of Chronic GVHD Cumulative incidence of chronic GVHD will be estimated (treating death and relapse as a competing risk) and curves will be compared using Gray's test. Estimates and confidence intervals will be provided for 6 and 12 months post-randomization.

5. Incidence of Systemic Infections

Frequencies of infections will be tabulated by site of disease, date of onset, and severity. The time to first serious infection will be described using the cumulative incidence function with death as the competing risk, and compared between treatments using Gray's test.

#### 6. Event-Free Survival

Event-free survival within each treatment group will be estimated using Kaplan-Meier methodology with event time being the earliest time a patient met one of the various criteria for failure or time of last follow-up for those patients not meeting the failure criteria. Pre-specified

time points of interest are 6 and 12 months post-randomization. Estimates and confidence intervals will be calculated for these time points.

#### 7. Overall Survival

Overall survival will be estimated using Kaplan-Meier methodology with event time being the earliest time of death or last follow-up. Pre-specified time points of interest are 6 and 12 months post-randomization. Estimates and confidence intervals will be calculated for these timepoints.

#### 8. Disease-Free Survival

Disease-free survival will be estimated using Kaplan-Meier methodology with event time being the earliest time a patient experienced a relapse of underlying malignancy, death or last followup. Pre-specified time points of interest are 6 and 12 months post-randomization. Estimates and confidence intervals will be calculated for these time points.

#### 9. GVHD-Free Survival

The proportion of patients alive and GVHD free at 6 and 12 months post-randomization will be estimated and compared between treatment groups using the Z test for comparing binomial proportions (or Barnard's Exact Unconditional test as appropriate).

#### 10. Non-relapse Mortality

Cumulative incidence of non-relapse mortality will be estimated (treating relapse as a competing risk) and curves will be compared using Gray's test. Estimates and confidence intervals will be provided for 6 and 12 months post-randomization.

#### 5.2.6. Analysis of Exploratory Endpoints

The following endpoints and subgroup analyses are considered exploratory and will be analyzed at a significance level similar to the secondary endpoints.

#### 1. Steroid Dose

Cumulative steroid dose will be described and compared between the treatment groups using a Wilcoxon Rank Sum test.

#### 2. Topical Therapy

The proportion of patients using either topical skin or topical GI steroids will be estimated within treatment group and by use at randomization. Among patients entering with no history of topical therapy, the proportion of patients initiating new topical treatment will be compared between treatment groups using the Z test for comparing binomial proportions (or Barnard's Exact Unconditional test as appropriate).

#### 3. Discontinuation of Immune Suppression

Cumulative incidence of immune suppression discontinuation will be estimated (treating death as a competing risk) and curves will be compared using Gray's test. Estimates and confidence intervals will be provided for Day 56, 6 and 12 months post-randomization.

4. Incidence of EBV-associated lymphoproliferative disorder

The incidence of EBV-associated lymphoproliferative disorder or EBV reactivation therapy will be described using the cumulative incidence function, treating death as the competing risk. Cumulative incidence curves will be compared between treatments using Gray's test.

#### 5. Incidence of hyperglycemia

Incidence of hyperglycemia and use of diabetes therapy at baseline, Day 28 and Day 56 will be estimated and compared between arms using a Z-test (or Barnard's Exact Unconditional as appropriate).

#### 6. Functional Myopathy

Change from baseline in functional myopathy score at Day 56 and 6-months post-randomization.

- i. Hip Flexor and Quadriceps Strength via handheld dynamometer
- ii. Two Minute Walk Test
- iii. 5-time Sit-to-Stand
- iv. Adult Myopathy Assessment Tool (AMAT)

These measures will first be assessed in patients with available data. Change from baseline within treatment group will be assessed using a Wilcoxon Signed Rank test at each timepoint. Change from baseline at each timepoint will be compared between treatment groups using a Wilcoxon Rank Sum test.

#### 7. Hyperlipidemia

Prevalence of hyperlipidemia as measured by fasting lipid panel and use of lipid-lowering agents at baseline, Days 28, 56 and 180 post-randomization will be compared between groups at each timepoint using a Z-test for binomial proportions (or Barnard's Exact Unconditional test as appropriate).

8. Post-transplant thrombotic microangiopathy

Cumulative incidence of post-transplant thrombotic microangiopathy will be estimated (treating death as a competing risk) and curves will be compared using Gray's test. Estimates and confidence intervals will be provided for 6 months post-randomization.

9. CMV-reactivation

Proportion of patients requiring therapy for CMV-reactivation by Day 56 post-randomization will be compared between treatment groups using a Z-test (or Barnard's Exact unconditional as appropriate).

10. Change in Patient-Reported Outcomes from Enrollment to Day 56, 6 months and 1 year. Participant self-reported measures will be assessed using the MDASI, FACT-BMT, and MOS SF-36 (or PedsQL for Pediatric patients) at enrollment, day 56, 6 months and 1 year. These will be scored according to the recommendations of the developers. Patient reported outcomes at each time point will be summarized using simple descriptive statistics (mean, SD). PRO among survivors at each time point will be compared between treatment arms in an initial analysis using two sample t-statistics. The missing data pattern of the PRO measurements will be examined using graphical techniques and logistic regression models conditional on survival. At each time point, estimates of the difference in PRO between the treatments conditional on survival at that

time point will be obtained using inverse probability of censoring weighting with independent estimating equations to account for missing data.

#### 5.2.7. Secondary Analysis of AA3 Patients:

A secondary analysis will consider study outcomes for AA3 patients (note patients with missing biomarker results will be excluded). Roughly 30 AA3 patients are expected to be enrolled with 15 receiving sirolimus while awaiting results and 15 receiving prednisone. Outcomes for these patients will be described by initial treatment to assess whether up front sirolimus vs. prednisone impacted outcome. Due to small numbers, the analysis will be primarily descriptive as we are not likely to have power to detect differences between the groups.

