Eligibility:	Patients of all ages with newly diagnosed standard-risk acute GVHD, diagnosed according to Refined Minnesota Criteria. All allogeneic donor sources and all conditioning regimens are allowed. Biopsy confirmation of GVHD is not required unless institutional practice mandates biopsy confirmation to make a GVHD treatment decision. Patients must have an absolute neutrophil count (ANC) greater than 500/µL. Patients must be able to tolerate oral or enterically-administered medication. Patients must have 5 mL blood samples collected for Ann Arbor Scoring. No previous systemic immune suppressive therapy for acute GVHD is allowed except topical corticosteroid use. Patients receiving sirolimus within 14 days of screening will be excluded. Patients with an active or recent (within 7 days) episode of transplant associated microangiopathy are not eligible. Patients with acute GVHD after donor lymphocyte infusion are not eligible. Patients with clinical presentation resembling de novo chronic GVHD or overlap syndrome are not eligible.	
Treatment Description:	Patients will be randomly assigned 1:1 to sirolimus vs. prednisone at 2mg/kg/day starting dose. Sirolimus will be loaded and then kept at maintenance dosing for target therapeutic levels for minimum duration through Day 56 post-randomization Prednisone will be kept at 2mg/kg/day x 3 days, and then tapered according to individual treating clinician judgment.	
Accrual Objective:	150 total patients will be enrolled and randomized 1:1 to sirolimus vs. prednisone. It is anticipated that $\sim$ 20% of randomized patients will have AA3 status or missing biomarker results resulting in 120 patients for the analysis of the primary endpoint.	
Accrual Period:	The estimated accrual period is 2 years.	
Study Duration:	Patients will be followed for 12 months following initiation of therapy.	

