GVHD ~25% NRM, and Ann Arbor 3 GVHD has >40% NRM. The scoring algorithm was validated in an independent test set of patients with aGVHD from the University of Michigan and the University of Regensberg, and in a separate validation set from multicenter Blood and Marrow Transplant Clinical Trials Network (BMT CTN) aGVHD treatment trials 0302 and 0802. Relapse rates do not differ between Ann Arbor scores and thus the differences in nonrelapse mortality translate into significant differences in survival. Differences in response to treatment account for the vast majority of differences in NRM. Patients with AA1 demonstrate 81% CR/PR at day 28 and AA2 patients demonstrate 68% CR/PR at day 28 (Figure 2). In contrast, high risk AA3 patients demonstrate 46% CR/PR at day 28. Furthermore, treatment responses for patients with AA3 GVHD are significantly less likely to be durable compared to AA1 and AA2 patients. Only 21% of AA3 patients remain in CR without flare at six months from diagnosis compared to 47% of AA1/2 patients (p<0.001). Importantly, similar proportions of patients are assigned to each Ann Arbor score in each of the three standard groupings of Glucksberg grades (I vs. II vs. III/IV). Thus, approximately 20% of all newly diagnosed GVHD cases have a high risk biomarker profile. These patients have poor responses to primary treatment, experience high NRM even when the clinical presentation is not severe, such as a <50% skin rash. Given their high likelihood of treatment failure, these patients are not good candidates for steroid sparing primary GVHD treatment trials. While compelling differences are observed in AA1/AA2 versus AA3 cohorts above, blood GVHD biomarkers have never previously been used to prospectively risk stratify patients.

In February 2017, the same group that developed the Ann Arbor scoring system published that the concentrations of two biomarkers, ST2 and REG3α, measured on day 7 after HCT predicted lethal GVHD. This group, now located at Mount Sinai School of Medicine, developed and validated the MAGIC (Mount Sinai Acute GVHD International Consortium) algorithm from

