#### 2.5.2. Ann Arbor Scoring

Immediately after randomization, the 5 ml of blood (red top for serum) will be shipped priority overnight for early morning arrival at the Biomarker Laboratory of the Icahn School of Medicine at Mount Sinai for biomarker analysis. Samples can be shipped Monday to Friday, and results can be delivered Tuesday through Saturday. Once received in the laboratory, the GVHD biomarkers used to assign the Ann Arbor GVHD score will be measured by ELISA using standard technical procedures in a CLIA certified laboratory. Processing the sample, measuring, and confirming the ELISA assay results take 4.5 hours (range 4-6 hours). Once the Ann Arbor

score is confirmed, the investigator at the participating center will be notified if the patient has AA1/2 biomarker risk, AA3 biomarker risk or missing biomarker results. Notification of the patient's Ann Arbor results will occur within 72 hours of study enrollment/randomization (usually within 48 hours).

Those with AA1/2 status will remain on their randomized therapy. AA3 patients and patients with missing biomarker results can continue on their randomized therapy, or another therapy, per the discretion of the treating physician. All patients, regardless of treatment received or biomarker status, must complete all planned study assessments. Patients with AA1/2 biomarker status and clinical standard risk will be included in the analysis for the primary endpoint. In contrast, patients with AA3 status or missing biomarker status will not be considered for the primary analysis, but will be included as a secondary descriptive analysis. GVHD response and therapy used in patients with AA3 status may be used in exploratory analyses to generate hypotheses for future high risk GVHD trials.

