# **3.1.1.** Response Definitions

Scoring of CR, PR, MR, NR and progression are in comparison to the participant's acute GVHD status (score) on the day of randomization.

**CR is defined as a score of 0 for the GVHD grading in all evaluable organs.** For example, for a response to be scored as CR at Day 56 or later, the participant must still be in CR on that day and have had no intervening additional therapy for an earlier progression, PR or NR.

**Partial response (PR) is defined as improvement in one or more organs involved with GVHD symptoms without progression in others.** For example, for a response to be scored as PR at Day 28 or later, the participant must still be in PR on that day and have had no intervening additional therapy for an earlier progression, PR or no response (NR).

Mixed response (MR) is defined as improvement in one or more organs with deterioration in another organ manifesting symptoms of GVHD or development of symptoms of GVHD in a new organ.

Progression is defined as deterioration in at least one organ without any improvement in others.

No response (NR) is defined as absence of any improvement or progression as defined. Patients receiving secondary therapy (including need to re-escalate steroid dose to  $\geq 2.5$  mg/kg/day of prednisone [or methylprednisolone equivalent of 2 mg/kg/day]) will be classified as non-responders. Patients who are assigned to the sirolimus arm who require initiation of systemic corticosteroids for the treatment of acute GVHD will be considered as non-responders for purposes of primary endpoint assessment.

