The number randomized assumes that 20% of randomized patients will have biomarker results indicating high risk disease (AA3) or missing biomarker results. Note that 60 analyzable patients per arm (150 randomized) will result in a lower bound of 15% assuming that the success rates in the two populations are equivalent. If sirolimus is 10% worse than the prednisone arm, the lower bound of the confidence interval will exceed 15%. Difference in Day 28 CR/PR rate across the two arms will be reported with associated 90% confidence interval, however no pre-planned difference or width of confidence interval will be used to indicate failure of either arm or serve

as a requirement for consideration of secondary endpoints (i.e. formal non-inferiority will not be declared in this trial). A key secondary endpoint is the proportion of patients in CR/PR with a steroid dose of  $\leq 0.25$  mg/kg by Day 28. Of the 95 placebo patients, 22.1% (95% CI 13.8% - 30.5%) achieved a CR/PR by Day 28 and were receiving  $\leq 0.25$  mg/kg. This estimate may not be reliable, however, as the taper for BMT CTN 0802 suggested a minimum of 0.25 mg/kg on Day 28 as such this may be an underestimate of the true rate. Using the upper end of the confidence interval, sixty patients per arm would provide 80.6% power (two-sided 5% type 1 error rate) to test for a difference of 25% between the two groups (30% Prednisone vs. 55% Sirolimus).

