**Day 56 Overall Mortality** 

If the true Day 56 overall mortality rate is in line with the expected rate (i.e. 10%), then the stopping guideline has a 5% probability of being triggered. If the true overall mortality rate is higher than expected (i.e. 25% by Day 56), then the stopping guideline has an 89% probability of being triggered (on average 12 months after opening when 30 patients have been enrolled).

No monitoring of secondary therapy delivered beyond prednisone will be performed in the prednisone arm, as this treatment is considered standard of care. We will prospectively monitor the rate of AA3 participants which is expected to be 20% of standard risk patients. This rate will be reported (with a 95% confidence interval) to the DSMB at each semiannual meeting to determine if the rate is higher than expected.

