## 2.8 Analysis Populations

### 2.8.1 Primary Analysis Population

Participants will be analyzed according to the intent to treat (ITT) principle for this study, i.e. according to the treatment groups to which they were randomized, regardless of whether the assigned treatment was administered. Any participant who receives a treatment randomization number will be considered to have been randomized. Since the primary interest of this study is treatment in participants with standard risk acute GVHD, the primary analysis population will consist of all randomized AA1/2 participants with treatment classified per the ITT principle.

The primary analysis for the primary, secondary, and exploratory endpoints will use the primary analysis population. A secondary analysis of the primary endpoint will be

performed, classifying participants by the initial treatment actually given. Another secondary analysis will consider primary and key secondary outcomes for all randomized AA3 participants classified per the ITT principle. An analysis of safety endpoints will also be conducted using the safety analysis population as described below. Analyses of each endpoint and population used will follow the analysis plan as described below in section 4 of this SAP.

If a participant is deemed not eligible for the study after study registration or randomization occurs, he will be excluded from all analysis populations.

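### In AA3 patients, a permitted change of therapy after the Ann Arbor result can be scored as sirolimus failure in the comparison by arm

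*Protocol*

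**What the plan says.** **Purpose and grouping.** Protocol 5.2.7 sets the aim: "Outcomes for these patients will be described by initial treatment to assess whether up front sirolimus vs. prednisone impacted outcome". It calls the analysis primarily descriptive, and SAP 4.3.11 calls it descriptive only. SAP 2.8.1 names the outcomes and the grouping: "Another secondary analysis will consider primary and key secondary outcomes for all randomized AA3 participants classified per the ITT principle". SAP 1.1.3 goes wider and refers to all study outcomes in AA3 participants.

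**Freedom to change therapy.** Protocol 2.5.2 says results reach the site within 72 hours of randomisation, usually within 48, and then: "AA3 patients and patients with missing biomarker results can continue on their randomized therapy, or another therapy, per the discretion of the treating physician". Protocol 4.2.1 repeats this. AA1/2 patients, by contrast, are to remain on their randomised drug.

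**Scoring rule.** Protocol 3.1.1 and SAP 4.1 contain the only Day 28 response definition. It includes: "Patients who are assigned to the sirolimus arm who require initiation of systemic corticosteroids for the treatment of acute GVHD will be considered as non-responders", a provision stated to be for the primary endpoint. In either arm, a patient who receives secondary therapy, including steroid re-escalation to at least 2.5 mg/kg/day, is also a non-responder. Treatment failure (Protocol 3.2.3, SAP 4.2.3) likewise counts the start of steroids for acute GVHD in the sirolimus arm.

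Neither document gives a response definition specific to AA3 patients, or says how a change of therapy made because of the AA3 result is to be scored.

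**The concern.** The steroid rule suits AA1/2 patients. They are meant to stay on sirolimus, so needing steroids tells us that sirolimus was not enough. In an AA3 patient, steroids may be started at 48 to 72 hours because of a laboratory result, before response to sirolimus can be judged. Protocol 2.5.7 itself asks for at least 4 days of the randomised therapy before secondary therapy is considered. Such a switch carries little information about response.

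The rule is also uneven between arms. A sirolimus-arm patient moved to prednisone can be failed by definition, while a prednisone-arm patient who stays on the same drug is judged on organ stage. A move from sirolimus to steroids is foreseeable, because Protocol 1.3 says of AA3 patients that "these patients are not good candidates for steroid sparing primary GVHD treatment trials".

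At stake is the reading of one table. It is the planned comparison by arm of what happens when sirolimus is started before AA3 status is known. Both documents warn about low power, but that warning does not tell a reader that the scoring may pull the comparison in one direction.

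**Working it through.** **Step 1. The plan's own figure.** The synopsis states "150 total patients will be enrolled and randomized 1:1 to sirolimus vs. prednisone". Protocol 5.2.2.2 gives the AA3 share, "which is expected to be 20% of standard risk patients". So 150 × 0.20 = 30 AA3 patients, and 30 / 2 = 15 per arm, which reproduces Protocol 5.2.7. It is an upper figure, because Protocol 5.1.5 uses the same 20% for a wider group: "The number randomized assumes that 20% of randomized patients will have biomarker results indicating high risk disease (AA3) or missing biomarker results". Patients with missing results are left out of the AA3 analysis.

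**Step 2. Inputs for the size.**
- True Day 28 CR/PR in AA3 patients: p = 46% (Protocol 1.3), assumed equal in both arms, so early sirolimus does no harm and no good.
- Share of AA3 sirolimus patients switched to steroids and scored as non-responders: s. Not in the documents, so shown from 0 to 100%.
- Share of AA3 prednisone patients given counted secondary therapy: t. Not in the documents; first set to 0.
- Switching is assumed unrelated to the response the patient would have had.

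**Step 3. Formula.** Scored sirolimus rate = p × (1 − s). Scored prednisone rate = p × (1 − t). Apparent deficit for sirolimus = p × (s − t).

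**Step 4. Results with t = 0.**

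| s | Scored sirolimus CR/PR | Scored prednisone CR/PR | Apparent deficit (points) | Expected sirolimus responders of 15 |
|---|---|---|---|---|
| 0% | 46% | 46% | 0 | 6.9 |
| 25% | 34.5% | 46% | 11.5 | 5.2 |
| 50% | 23% | 46% | 23 | 3.5 |
| 75% | 11.5% | 46% | 34.5 | 1.7 |
| 100% | 0% | 46% | 46 | 0 |

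**Step 5. Sensitivity.**
- True rate: if p is 36% or 56% (assumed bracket), each 25% switched costs 0.25 × 36 = 9 or 0.25 × 56 = 14 points.
- Prednisone arm: with s = 50% and t = 25%, the deficit is 46 × (0.50 − 0.25) = 11.5 points, half the 23 points at t = 0.
- Who is switched: if the switched patients would have responded less often than 46%, fewer true responders are reclassified and the deficit is smaller; if more often, it is larger.

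**Step 6. Scale.** With 15 per arm and 46% in each, the half-width of a 90% interval for the difference is 1.645 × √(2 × 0.46 × 0.54 / 15) = 0.30, about 30 points.

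**Step 7. Which outcomes are touched.** The rule acts on Day 28 CR/PR and on treatment failure, if that is tabulated for AA3 patients. The endpoint combining CR/PR with a steroid dose of 0.25 mg/kg/day or less has a stated exception for low-dose prednisone on the sirolimus arm (Protocol 3.2.1), so it is affected less clearly. Overall survival and non-relapse mortality are not scored by the rule.

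**The case against.** A reader might infer that the AA3 table is bound to show a large sirolimus deficit. The documents do not support that. They give no switching rate, and they let AA3 patients stay on the randomised drug. The remark in Protocol 1.3 makes switching plausible but does not predict how common it will be. With no switching there is no artefact, and 46 points needs every sirolimus patient to switch.

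A reader might also infer that the prednisone arm cannot be failed by a change of therapy, or that any steroid use fails a sirolimus patient. Neither is right. Counted secondary therapy fails patients in both arms, and AA3 patients respond poorly, so it may well occur on prednisone. The steroid rule covers steroids for acute GVHD, and Protocol 3.1.1 speaks of patients who *require* them. Whether a discretionary switch on a laboratory result meets that word is not stated. This does not rescue the plan: under the assumptions above, if all 15 switched, the same patients could be scored at 46% on one reading and 0% on the other, and the documents do not choose. The treatment-failure definition in Protocol 3.2.3 does not use the word at all.

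Finally, a reader might infer that this table decides whether sirolimus can be started before the biomarker is known, or that it weakens the trial's main result. No passage gives it that role. The hypothesis-generating aim in Protocol 2.5.2 attaches to exploratory use of AA3 response and therapy data. The analysis is descriptive, its random error at 15 per arm exceeds the assumed artefact at half switching, and the AA1/2 primary analysis is separate. Survival and non-relapse mortality are already study outcomes that readers can turn to. These points limit the consequence. They do not remove the uneven scoring.

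**Conclusion.** The concern holds in a limited form. As written, the AA3 analysis can score a switch prompted by the Ann Arbor result as a sirolimus non-response, while a prednisone patient who stays on the same drug is judged on organ stage. That can bias the comparison the protocol says it wants to make.

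The apparent deficit is 46% × s: anywhere from 0 to 46 points, with 23 points at half switching. This rests on equal true response of 46% in both arms, no counted secondary therapy on prednisone, switching unrelated to response, and the reading that a biomarker-driven switch counts as requiring steroids. It shrinks if prednisone AA3 patients also receive counted secondary therapy. The direction of the concern follows from the text; its size cannot be known from the documents.

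The change is worth making because it removes a bias at little cost, although the harm is confined to the reading of a small descriptive table.

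**What to change.** In Protocol 5.2.7 and SAP 2.8.1 and 4.3.11, for AA3 patients by assigned arm:

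1. Report Day 28 organ-stage response against the day of randomisation, regardless of any change of therapy, beside the rule-based CR/PR.
2. Tabulate by arm the number, day and type of therapy changes after the Ann Arbor result. In the rule-based CR/PR and in treatment failure, label switches made on the biomarker result separately from failures. The listed assessments record the therapy but do not mention the reason for a change, so state in advance how a biomarker-driven switch will be identified, for example by its date relative to the result.
3. Align the protocol's grouping by initial treatment with the SAP's grouping by intention to treat.

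The cost is SAP wording and a few extra rows in a descriptive table. Protocol 2.5.2 and 4.4 already require staging, steroid dose and second-line therapy to be recorded in all patients whatever therapy they receive. No treatment rule changes. One limit should be stated in the table: organ-stage response regardless of therapy then reflects a short sirolimus exposure followed by whatever came next, not sirolimus alone.
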